8.0 Study Withdrawal/Discontinuation

Subjects may withdraw from the study at any time and should notify study personnel if they wish to withdraw from the study. Subjects may request their biological samples to be destroyed at any time. However, any data or biological samples that have already been used for research cannot be destroyed. Subjects may be discontinued from the study at the discretion of the investigators' (possible reasons listed below). Subjects will receive financial compensation for the visits that they complete.

Possible reasons for withdrawal/discontinuation from study include, but are not limited to:

- Noncompliance with treatment or procedures
- Decision by participant/participant withdraws consent
- Lost to follow-up
- Starting a medication that would exclude the subject (see exclusion criteria)
- Development of a significant medical condition specified in the exclusion criteria
- In female subjects, becoming pregnant during study
- Significant adverse event deemed by investigator to preclude continued participation

9.0 Statistical Considerations

Subjects who are overweight or obese (n=20) will be recruited through this IRB. To analyze study hypotheses, and for comparison to normal weight individuals, we will share data from the study cohort of [name] (IRB #151943). This will include identical data acquired from at least n=20 subjects who are normal weight (18 to <25 kg/m²) and who meet identical inclusion/exclusion criteria.

Statistical analysis procedures for Aim 1: Statistical analyses will be performed by key study personnel and members of the Center for Quantitative Sciences at the VUMC. The primary statistical objective of Aim 1 is to test the hypothesis that adults who are salt sensitive have higher baseline tissue sodium relative to adults who are not salt sensitive. To test this, we will divide participants into those who are salt sensitive (SS, ≥5 mmHg change in mean arterial pressure ΔMAP following high salt diet compared to low salt diet) or not salt sensitive (NSS, <5 mmHg ΔMAP), according to a review of methods and recommendations from Kurtz et al.²⁶. The metric ΔMAP represents a continuous variable of SSBP. A Mann Whitney U test will be applied to determine whether tissue sodium content is significantly different in SS and NSS groups. Based on a prior study of tissue sodium storage in adults who are hypertensive (n=10)

or normotensive (n=12)¹⁹ we anticipate a similar difference in tissue sodium of 6±4 (mean ± standard deviation, mmol/L) between SS and NSS adults. Our study is designed to provide at least 80% power to detect differences in tissue sodium with a two-sided significance of p<0.05.

Our secondary statistical objective of Aim 1 is to test the hypothesis that tissue sodium content and potential risk factors for SSBP, including biological sex, age, and tissue fat/water fraction as a sensitive surrogate of BMI, are related to Δ MAP as a continuous variable. We will apply multivariable regression analysis using tissue sodium, fat/water fraction, biological sex, and age as independent variables, and Δ MAP as the dependent variable among all participants. With a sample size of 40 , we should be able to evaluate the four predictors of Δ MAP (each with one degree of freedom) without over-fitting the model.

Statistical analysis procedures for Aim 2: The primary statistical objective of Aim 2 is to test the hypothesis that tissue sodium content has an inverse relationship with lymphatic flow velocity, which depends on a person's salt sensitivity. To test this hypothesis, we will apply multivariable regression analysis using tissue sodium as the dependent variable, and lymphatic flow velocity, Δ MAP, biological sex, and age as independent variables among all participants.

Statistical analysis procedures for Aim 3: The primary statistical objective of Aim 3 is to test the hypothesis that elevated tissue sodium content is associated with reduced renal perfusion, which depends on a person's salt sensitivity. We will apply similar statistical analyses as Aim 2 to evaluate the relationships between renal cortical perfusion and peripheral tissue sodium content in adults evaluated for salt sensitivity.

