While renal dysfunction is implicated in SSBP⁹, emerging evidence suggests that lymphatic mechanisms additionally regulate tissue salt storage and blood pressure¹⁰ and may contribute significantly to systemic vascular resistance^{11, 12}. The lymphatic system is a central component of the body's circulatory system, functioning in the regulation of tissue sodium homeostasis, in the clearance of high-density lipoproteins¹³ and metabolism of fatty acids⁷. Lymphatic clearance of tissue salt may represent an extra-renal system¹⁴ capable of regulating blood pressure^{15, 16} such that inhibition of this pathway is implicated in salt-sensitive hypertension^{17, 18}. Patients with essential hypertension, who were not evaluated for salt sensitivity, display elevated tissue sodium in peripheral tissues¹⁹. Similar profiles of elevated tissue sodium have been reported in patients with chronic kidney disease²⁰. Additionally, impaired lymphatic clearance and renal dysfunction may also contribute to obesity^{21, 22}, which is an established risk factor for cardiovascular disease. Our overarching hypothesis is that impaired lymphatic and renal vascular function is associated with elevated tissue sodium and fat storage in persons with SSBP.

Magnetic resonance imaging (MRI) tools for measurement of lymphatic and renal function associated with tissue sodium and fat deposition

The critical limitation to interrogating lymphatic and renal clearance of sodium in vivo rests with a lack of noninvasive imaging technologies sensitive to sodium, lymphatic, and renal physiology. To address these limitations, we have recently developed a novel, noninvasive magnetic resonance (MR) lymphangiography technique²³ and applied standardized MRI protocols for measuring tissue sodium and related fat deposition in adults with impaired lymphatic clearance. We found evidence of lymph stasis and tissue salt deposition that

correlated with local subcutaneous adipose tissue volume²⁴. Here, we will use noninvasive MRI to test whether similar lymphatic pathways are impaired in persons with SSSB, leading to tissue salt and fat storage, in comparison to the involvement of renal dysfunction in SSSB tissue profiles.

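### The Aim 2 and Aim 3 models enter ΔMAP only as a main effect, so they do not test whether the sodium slopes depend on salt sensitivity; if ΔMAP is a consequence of sodium, they also understate those slopes.

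*Protocol*

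**What the plan says.** The Aim 2 paragraph of protocol 9.0 posits an "inverse relationship with lymphatic flow velocity, which depends on a person's salt sensitivity". The model offered for it takes tissue sodium as the outcome, with "lymphatic flow velocity, Δ MAP, biological sex, and age as independent variables among all participants". No product of flow and ΔMAP is listed. Aim 3 makes the matching claim for renal perfusion and says only "We will apply similar statistical analyses as Aim 2", without writing out a model.

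Aim 1 in the same section uses the two variables both ways round. Its secondary model has "tissue sodium, fat/water fraction, biological sex, and age as independent variables, and Δ MAP as the dependent variable among all participants". Its primary test puts sodium on the outcome side, to "determine whether tissue sodium content is significantly different in SS and NSS groups", with the groups formed by a ΔMAP cut-off.

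SAP 6.1 plans something else. For Aim 2 it gives correlations in salt-sensitive (SS) and salt-resistant (SR) adults. It then adds a robust-error regression with an interaction, to see whether the flow-sodium slope differs between the groups, adjusted for sex and fat/water fraction. Continuous blood-pressure change is not a covariate. For Aim 3 it gives correlations in SS and SR adults, but its interaction compares the flow slope with the perfusion slope inside the SS group.

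**The concern.** A relation that depends on salt sensitivity is effect modification: the slope of sodium on flow changes with ΔMAP. A main effect of ΔMAP moves the intercept and leaves one common slope, so no coefficient in the protocol's model answers the question. This holds whatever the causal order.

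The second issue is conditional. If impaired clearance raises stored sodium and stored sodium raises salt sensitivity, ΔMAP is a consequence of the Aim 2 outcome. Conditioning on it then removes part of the flow effect, and removes more the stronger the sodium-ΔMAP link that Aim 1 hopes to find.

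At stake are the primary objectives of two aims. As written, the protocol could report a slope that is hard to interpret and still have no test of its stated hypothesis. Because the SAP differs, the analyst would also have to choose between models after seeing the data.

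**Working it through.** **1. The plan's own power figures.** The protocol gives no power for the Aim 2 and 3 regressions. The SAP claims 80% for a correlation of 0.49 with 16 per group (Aim 2) and 20 per group (Aim 3), two-sided 0.05. By Fisher z, power = Φ(atanh(r)·√(n−3) − 1.96), with atanh(0.49) = 0.536.

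- n = 16: 48.9%. n = 20: 59.9%.
- Pooled n = 32: 82.3% (80.1% with the Spearman variance factor 1.06). Pooled n = 40: 90.3%.

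So the Aim 2 figure reproduces only for the pooled sample, and the Aim 3 figure for neither. This is a separate matter, but it shows that the SAP's within-group tests are weaker than stated.

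**2. What each document tests.**

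| Question | Protocol 9.0 | SAP 6.1 |
|---|---|---|
| Flow-sodium relation | Regression with ΔMAP, sex, age | Correlations in SS and SR adults |
| Does the flow slope differ by salt sensitivity? | No term | SS/SR interaction; sex, fat/water fraction |
| Perfusion-sodium relation | Similar to Aim 2 | Correlations in SS and SR adults |
| Does the perfusion slope differ by salt sensitivity? | No term | No term |

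**3. Attenuation if the order is flow → sodium → ΔMAP.** Inputs: r = 0.49 in size for flow-sodium (the SAP's sodium-fat/water correlation, which it carries over to flow and perfusion); n = 40 (protocol 9.0); sodium-ΔMAP correlation c, assumed. One guide to c is the anticipated SS/NSS difference of 6±4 mmol/L: d = 6/4 = 1.5, so with a 50:50 split the point-biserial r = 1.5/√(1.5² + 4) = 0.60, or about 0.75 on the continuous (biserial) scale.

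Fraction of slope kept = (1−c²)/(1−r²c²). Partial r = r·√[(1−c²)/(1−r²c²)]. Power uses n−3−k, with k = 2 without ΔMAP (sex, age) and k = 3 with it. Without ΔMAP, power is 88.7%.

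| c | Slope kept | Partial r | Power with ΔMAP |
|---|---|---|---|
| 0.3 | 93% | 0.473 | 84.9% |
| 0.5 | 80% | 0.438 | 78.1% |
| 0.6 | 70% | 0.410 | 71.9% |
| 0.75 | 51% | 0.348 | 56.4% |

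Simulation (10,000 trials, least squares, sex and age in the model) agrees: the slope goes from −0.49 to −0.455, −0.341 and −0.247 at c = 0.3, 0.6 and 0.75.

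**4. The same adjustment under other orders** (simulated, n = 40).

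- Salt sensitivity upstream of sodium and independent of flow: the slope is unchanged, and power rises from 89% to 92% (c = 0.3) or 99% (c = 0.6).
- Salt sensitivity a common cause of flow and sodium, no true flow effect (assumed flow-ΔMAP correlation −0.5, c = 0.6): omitting ΔMAP rejects in 45% of trials; including it rejects in 4.9%.

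**5. Power for the interaction, as a guide.** Suppose r = 0.49 in one group and 0 in the other. Power = Φ(0.536/√(1/(n₁−3)+1/(n₂−3)) − 1.96).

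- 20 and 20: 0.536/0.343 = 1.563, power 35%.
- 16 and 16: 0.536/0.392 = 1.367, power 28%.
- 30 and 10 (close to the 74% prevalence in protocol 1.0): 0.536/0.424 = 1.264, power 24%.

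**The case against.** A reader might infer that the ΔMAP covariate is simply wrong, that it must bias the slopes toward zero, and that it should be dropped. The documents do not support that.

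- They are mixed on causal order. In protocol 1.0, lymphatic clearance of tissue salt is described so that "inhibition of this pathway is implicated in salt-sensitive hypertension", which puts pressure downstream, and Aim 1's secondary model agrees. But that objective speaks only of variables being related, Aim 1's primary test has sodium as the outcome, and the background also describes impaired lymphatic pathways in people with the trait as leading to salt storage.
- Timing does not settle it: the MRI may come before the diets or at least a week after the second one, and the SAP schedules it at day 28 or later.
- Under a common-cause structure, dropping ΔMAP does the damage (step 4).

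The objection stands against any unconditional claim of bias. Three further cautions also stand. Aim 3's covariates are inferred from the word similar. The 0.49 was observed for a different pair of variables, and the guide to c carries over a hypertensive-versus-normotensive contrast. The SAP model is not free of conditioning either, since its groups are defined by blood-pressure change.

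It might also be said that the SAP already repairs the omission. It does so for Aim 2 only. Its expectation of significance in SS but not in SR is not itself a test of difference, and its Aim 3 interaction answers another question.

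**Conclusion.** The firm part needs no causal assumption: protocol 9.0 states a dependence on salt sensitivity and lists no term that tests it. The SAP supplies one for flow but none for perfusion, and the two documents specify different Aim 2 models.

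The attenuation is conditional. If ΔMAP is a consequence of sodium, the flow slope loses about 7% to 49% and power falls from about 89% to between 85% and 56%. This assumes c between 0.3 and 0.75, r = 0.49, linear normal relations, sex and age unrelated to the other variables, and no dropout. If salt sensitivity is upstream, adjustment costs nothing or helps. The perfusion slope would behave in the same way only if Aim 3's unlisted model carries ΔMAP. The point should be corrected before analysis; it does not show that the planned slopes are biased.

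**What to change.** 1. In protocol 9.0 (Aims 2 and 3) and in the SAP's Aim 3, name the flow×ΔMAP and perfusion×ΔMAP interaction, or the SS/SR version, as the test of dependence. Choose one version as primary.
2. Write out the Aim 3 model, and make the protocol and SAP models and covariates identical. Use one salt-sensitivity measure: the protocol works from ΔMAP, high-salt compared with low-salt, while the SAP defines a ΔBP from systolic pressure as low-salt minus high-salt.
3. State the assumed causal order of flow or perfusion, sodium and ΔMAP.
4. Report each main slope with and without ΔMAP, and say in advance which is primary under that order. Do not read the lower-order coefficient of the interaction model as the main slope.
5. Do not make fat/water fraction a required covariate of the main slope model. Protocol 1.0 describes fat storage as another result of impaired clearance. If flow-fat correlation were also −0.49 (assumed), the flow coefficient given fat would be (−0.49+0.24)/(1−0.24) = −0.33, with power of about 51%.
6. Report the interaction as an estimate with a confidence interval, and acknowledge its limited power.

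Cost: wording in both documents and one or two extra model fits per aim; no new data or visits.

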10.0 Privacy/Confidentiality Issues

Strict confidentiality will be maintained to the fullest extent by the research team, including keeping all data in a secure, locked cabinet with limited access and/or password protected databases, i.e. REDCap. All specimens will be coded after they are obtained and the code key kept in a locked cabinet. Blood samples will be coded anonymously to remain confidential and identifiers will be kept in a separate, secure, locked location. Samples may be shared with third parties outside of Vanderbilt for future testing but will remain anonymous to the recipient. If samples are accidentally lost, subjects will not be re-contacted to provide a substitute sample. The investigators will not be obligated to keep contact information to re-contact the subject. Subjects may contact the principal investigator at any time to request that samples be destroyed.

The data files generated by the MRI scanner and L-Dex software are coded using a project name and unique number generated sequentially. Only the investigators will have the key to the subject codes. Image analysis will use the coded files. The safety surveys described above include questions about sensitive health issues. This information will remain with the signed

consent form in a secured area near the scanner. These records will remain in the investigators' possession for ten years following the termination of the study and will then be destroyed.

11.0 Abbreviations

²³NA: sodium

AHA: American Heart Association

BMI: body-mass index

MAP, Δ MAP: mean arterial pressure, or change in mean arterial pressure following high salt diet compared to low salt diet

CRC: Clinical Research Center

eGFR: estimated Glomerular Filtration Rate

FDA: food and drug administration

MRI: magnetic resonance imaging

RAAS: renin-angiotensin-aldosterone system

REDCap: Research Electronic Data Capture

SSBP: salt sensitive blood pressure

VICTR: Vanderbilt Institute for Clinical and Translational Research

VUIIS: Vanderbilt University Institute of Imaging Science

4.1 Preface

Salt sensitive blood pressure preferentially affects black Americans

Salt sensitive blood pressure (SSBP) is a physiologic phenotype defined by a parallel change in blood pressure in response to dietary salt load. SSBP is fundamentally related to the body's inability to clear salt, leading to elevated blood pressure and a life-long increased risk of cardiovascular disease. SSBP was determined to be an independent risk factor for developing cardiovascular disease in hypertensive patients almost two decades ago¹, and more recently SSBP was found to portend all-cause mortality². It is a prevalent condition that affects up to 50% of normotensive, 75% of hypertensive³, 74% of black American adults⁴, and is estimated to be 6% more prevalent among females than males^{5, 6}. Black Americans are preferentially affected by this phenotype and represent one of the most at-risk population for cardiovascular diseases related to SSBP. Salt sensitivity is increased with the occurrence of metabolic syndrome associated with abdominal obesity⁷ and insulin resistance⁸. Current tests for SSBP require dietary salt loading, are time-intensive and, more importantly, provide limited mechanistic information on the incompletely characterized mechanisms of tissue salt storage.

4.2 Scope of the analyses

Our overarching hypothesis is that impaired lymphatic clearance is associated with elevated tissue sodium and adipose storage in persons with SSBP. The overall goal of this work is to apply noninvasive, clinical imaging tools to assess the biological systems involved in the pathophysiology of tissue salt storage, which will enable future investigations of mechanisms and development of treatment strategies for SSBP in a clinical population.

5 Study Objectives

5.1 Impacts

Impact of Aim 1: Over half of the American population is estimated to be salt sensitive and yet research of this pathophysiology is limited by time-consuming and specialized protocols to identify salt sensitivity. 1) A radiologic phenotype of SSBP, based on unique distributions of tissue salt and adipose content, has the potential to serve as a surrogate test for salt sensitivity. Methods applied here can be performed in routine clinical imaging centers, making its potential translation to clinical research possible. 2) Establishing a radiologic phenotype of salt sensitivity is a necessary prerequisite to studying mechanistic hypotheses *in*

vivo about how tissue salt is stored and its relationship to a known risk factor for cardiovascular disease, adiposity.

Impact of Aim 2: Identifying for the first time the extent of lymphatic dysfunction in SSBP could motivate the exploration of understudied lymphatic mechanisms of salt sensitivity, as current models of salt sensitivity are incomplete. Successful completion of this aim will provide the necessary lymphatic imaging technologies to evaluate emerging therapies that hold promise for improving lymphatic pumping and lymphangiogenesis²⁸, and potentially tissue sodium clearance to improve the management of patients with salt sensitivity and increased risk of cardiovascular disease.

Impact of Aim 3: Localized, noninvasive imaging metrics of renal circulation within the cortex, where sodium-filtering nephrons are located, relative to peripheral tissue sodium storage have potential to portend salt sensitive hypertension if their relationship to SSBP is established.

6 Study Methods

6.1 Data Acquisition and Analysis

Blood Pressure Measurements. During screening and active treatment, outpatient BP will be measured with an aneroid sphygmomanometer (Welch Allyn, Skaneateles Falls, NY), using the appearance and complete disappearance of the Korotkoff sounds (K1 and K5) as systolic blood pressure and diastolic blood pressure. The mean of three seated measurements will be used. During study days, BP will be measured using an automated oscillometric recording device (Dinamap, Critikon, Carlsbad, CA) while the subjects are supine. The mean of three measurements one min apart will be used. Change in blood pressure as a primary outcome measure of salt sensitivity will be calculated as the mean arterial systolic pressure during LSD minus the mean arterial systolic pressure during HSD (Δ BP, mmHg, in absolute units).

Standardized ^{23}Na (sodium) MRI. Mentor [name], who has experience with multi-nuclear imaging and development, will oversee application and analyses. Sodium MRI will be acquired from the dominant upper and lower extremities using the standardized clinical sodium MRI protocol⁴⁰ previously used to determine sodium stores in hypertensive patients²⁶. Briefly, the subject's calf will rest on a platform embedded with four standard sodium solutions (aqueous NaCl in the physiologic range of tissue sodium content 10-40 mmol/L) inside a quadrature coil tuned for sodium signal reception, and the sodium MRI protocol performed. Next, the subject will be repositioned to place their forearm inside the coil, and sodium MRI performed. Each sodium image acquisition time is approximately 15 minutes. The MR signal intensity in tissues will be calibrated to signal intensity within the standard sodium solutions to produce a map of standardized tissue sodium content (Figure 2B-C). Standardized tissue sodium content (mmol/L) will be measured in the muscle (primary observable of interest) but will also be quantified in skin and subcutaneous adipose tissues for exploratory analyses.

[figure not shown]

Figure 2. (A) Validation of MR lymphangiography with clinical gold-standard lymphoscintigraphy in a patient with edema of the left leg. Gray arrow=pubic marker, black arrow=knee marker. Lymph stasis is visible 40 min post-contrast injection on lymphoscintigraphy, which can also be visualized in 10 min at higher spatial resolution using MR lymphangiography (blue box). Note that the position was repositioned between scans with these different modalities, however the proximity of stasis (hypointensity) is identical. The red dashed line indicates the location of sodium and adipose imaging. **(B-C)** MRI of tissue sodium and adiposity in the calf of a patient with lymphatic dysfunction due to lipedema and a female control matched for age, race, and BMI. Structural measures of calf circumference and subcutaneous adipose tissue (SAT) area are similar. However, total tissue fat/water fraction is elevated (lipedema vs. control values, 0.95 vs. 0.87 ratio). Tissue sodium content is higher in the patient with lipedema in all regions, including skin (15.7 vs. 12.6 mmol/L, arrow), SAT (13.3 vs. 8.2 mmol/L, arrowhead), and muscle (19.8 vs. 14.3 mmol/L, circle). **These findings demonstrate the potential for tissue sodium and adiposity to indicate lymphatic impairment which may have relevance to SSBP.**

Body composition MRI. Mentor [name] will oversee application of the AMRA® Body Composition Protocol available at our center. The AMRA® Body Composition Protocol employs the Dixon MRI method for separating fat and water signals from a single acquisition to provide fat-weighted and water-weighted images. We will apply this method optimized for whole-body imaging from the head to ankle. Images in the legs will be analyzed for this study's purpose, and whole-body image acquisitions preserved for potential future analyses of visceral fat, intramuscular fat, total abdominal fat index, lean muscle tissue, and liver fat. Here, we will use automated image-processing routines developed in our preliminary study¹⁰ to measure **tissue fat/water fraction (ratio)** in the identical slice where sodium imaging was acquired. Tissue fat/water fraction will be calculated as the ratio of the volume of subcutaneous and intramuscular adipose compared to the volume of muscle and skin tissues.

Statistical analysis procedures for Aim 1:

Statistical analyses will be overseen by [name] and members of the Center for Quantitative Sciences

(see mentor support letter). The primary statistical objective of Aim 1 is to test the hypothesis that adults who are salt sensitive have elevated baseline tissue sodium relative to adults who are not salt sensitive. To test this, we will apply a previously-published, informed cutoff to dichotomize participants into those that are salt sensitive (SS, ≥ 5 mmHg reduction in Δ BP depletion) or salt resistant (SR, < 5 mmHg reduction in Δ BP), according to a review of methods and recommendations from Kurtz *et al.*¹¹. The metric Δ BP represents a continuous variable of SSBP; tests for normality and homoscedasticity will be made. Depending on normality, a Mann Whitney U test or a Student's t-test will be applied to determine whether muscle sodium content is significantly different in SS and SR groups, matched for race and accounting for biological sex as a covariate. Based on a prior study of tissue sodium storage in adults with hypertension (n=10) and normotensive (n=12)²⁶ we anticipate a similar difference in tissue sodium of 6 ± 4 (mmol/L) between SS and SR adults. With a sample size of 20 in each group, our study design will provide at least 80% power to detect differences in tissue sodium with a two-sided significance of $p<0.05$.

Our secondary statistical objective of Aim 1 is to test the hypothesis that muscle sodium content and potential risk factors for SSBP, including biological sex and tissue fat/water fraction as a sensitive surrogate of BMI, are related to Δ BP as a continuous variable. We will apply multivariate regression analysis using muscle sodium, fat/water fraction, and biological sex as independent variables, and Δ BP as the dependent variable among all participants. With a sample size of 40, we will have sufficient power to evaluate three predictors of Δ BP at the

Statistical analysis procedures for Aim 2:

The primary statistical objective of Aim 2 is to test the hypothesis that tissue sodium content is elevated in tissues affected by impaired lymphatic flow. To test this hypothesis, the same statistical considerations outlined in Aim 1 will be applied. Next, we will calculate either the Pearson's- r or Spearman's-rho correlation coefficient, depending on normality, between lymphatic flow velocity and tissue sodium content in adults who are SS or SR and matched for age, biological sex, and BMI. The correlation coefficient and adjusted p-values and 95% confidence intervals will be reported for each test, with the hypothesis that the relationship will be significant in SS but not SR individuals. Based on our preliminary data in normotensive black women who display a Spearman's-rho=0.49 between tissue sodium and fat/water fraction (**Table 1**), we anticipate a similar or greater correlation with lymphatic function; with 16 subjects in each group, our design will provide 80% power to detect a correlation with two-sided significance of $p<0.05$ between tissue sodium content and lymph flow velocity. To test whether the relationship between lymphatic flow velocity and muscle sodium is unique for the different groups, a linear regression with robust errors and an interaction term will be applied. The covariates will be biological sex and fat/water fraction. The coefficient for the interaction will be quantified as the difference between the slopes.

Statistical analysis procedures for Aim 3: The primary statistical objective of Aim 3 is to test the hypothesis that elevated tissue sodium content is associated with reduced renal perfusion in adults with SSBP. To test this hypothesis, we will calculate either the Pearson's- r or Spearman's-rho correlation coefficient, depending on normality, between renal cortical perfusion and peripheral tissue sodium content in adults who are SS or SR and matched for age, race, and BMI, and accounting for biological sex as a covariate. The correlation coefficient and adjusted p-values and 95% confidence intervals will be reported for each test. Based on our preliminary data in normotensive black women who display a Spearman's-rho=0.49 between tissue sodium and fat/water fraction (**Table 1**), we anticipate a similar or greater correlation with renal perfusion; with 20 subjects in each group, our design will provide 80% power to detect a correlation with two-sided significance of $p<0.05$ between tissue sodium content and renal cortical perfusion. Next, to compare the relationships in the SS group between i) tissue sodium and lymph flow velocity and ii) tissue sodium and renal cortical perfusion, a linear regression for each relationship with robust errors and an interaction term will be applied. The covariates will be biological sex and fat/water fraction. The coefficient for the interaction will be quantified as the difference between the slopes.

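### The sign of the salt-sensitivity variable is defined inconsistently: the protocol implies high salt minus low salt, the SAP formula reverses the order, and the SAP cutoff cannot be computed as written

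*SAP*

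**What the plan says.** Four places define the variable or its cutoff.

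- **Protocol 9.0, Aim 1.** Salt sensitive (SS) is "≥5 mmHg change in mean arterial pressure ΔMAP following high salt diet compared to low salt diet"; not salt sensitive is "NSS, <5 mmHg ΔMAP".
- **Protocol 11.0.** ΔMAP is a "change in mean arterial pressure following high salt diet compared to low salt diet". The order suggests high minus low, but there is no formula, no sign, and no word such as rise or increase.
- **SAP 6.1, Blood Pressure Measurements.** The primary measure of salt sensitivity is the low-salt pressure "minus the mean arterial systolic pressure during HSD (Δ BP, mmHg, in absolute units"). This is low minus high.
- **SAP 6.1, Aim 1.** SS is "≥ 5 mmHg reduction in Δ BP depletion" and salt resistant (SR) is "< 5 mmHg reduction in Δ BP".

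Both documents give the concept in their background text. SAP 4.1 says salt-sensitive blood pressure is "defined by a parallel change in blood pressure in response to dietary salt load", that is, pressure moves the same way as salt.

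The variable sets the Aim 1 groups in both documents and the SS/SR groups in SAP Aims 2 and 3. It is the dependent variable in the Aim 1 secondary regression. In the protocol's Aim 2 regression, and in the similar Aim 3 analysis, it is a predictor. SAP 9.1, where the primary analysis should be fixed, still holds template instructions and so settles nothing.

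**The concern.** Three things do not fit together. The protocol and the SAP formula subtract in opposite orders. The SAP's closing words about absolute units may mean mmHg rather than percent, or an unsigned value. The SAP cutoff asks for a reduction in a quantity that is already a difference.

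Two analysts could therefore label the same person differently, or report the same association with opposite signs, and each could cite the plan. An inverse responder placed in the SS group contradicts the concept in SAP 4.1 and mixes opposite responses in the group that the primary hypothesis concerns. The study is unblinded (SAP 6.3), so a sign rule settled at analysis would be settled with data in view.

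**Working it through.** **1. The plan's own figure.** SAP 6.1 gives a sodium difference of 6, SD 4, 20 per group and two-sided 0.05, and claims at least 80% power. The normal approximation gives Φ(6/(4·√(2/20)) − 1.96) = Φ(4.74 − 1.96) = 99.7%. The claim holds and does not depend on the sign of ΔBP.

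**2. Each reading applied to two illustrative participants.** A has 92 mmHg on high salt and 85 on low salt. B, an inverse responder, has 85 on high salt and 92 on low salt.

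| Reading | A | B |
|---|---|---|
| Protocol, signed high minus low | +7, SS | −7, NSS |
| Protocol, change taken as a magnitude | 7, SS | 7, SS |
| SAP formula, unsigned | 7, SS | 7, SS |
| SAP formula, signed, cutoff of 5 applied literally | −7, SR | +7, SS |
| SAP Aim 1, reduction read as a fall from high to low salt | fall of 7, SS | no fall, SR |

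The first and last rows agree with each other and with SAP 4.1. Two of the others admit B to the SS group, and the fourth row also expels A.

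**3. Regressions.** If the SAP sign is kept, ΔBP = −Δ, where Δ is high minus low. With the same pressure and covariates, reversing an outcome reverses every coefficient, and reversing a predictor reverses its own. Magnitudes, p-values and fit are unchanged.

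**4. How many people an unsigned reading would move.** The documents give no SD for the pressure change, so I assume Δ is normal with SD s = 6 to 8 mmHg. The true SS share p is 50% (the upper figure for normotensive people) or 74% (black American adults), both from Protocol 1.0 and SAP 4.1. The mean is set so that P(Δ ≥ 5) = p, giving μ = 5 + s·z(p). The inverse-responder share is Φ((−5 − μ)/s), and the analysis set is 40.

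| p | s | μ | Inverse share | Of 40 |
|---|---|---|---|---|
| 50% | 6 | 5.00 | Φ(−1.67) = 4.8% | 1.9 |
| 50% | 8 | 5.00 | Φ(−1.25) = 10.6% | 4.2 |
| 74% | 6 | 8.86 | Φ(−2.31) = 1.0% | 0.4 |
| 74% | 8 | 10.15 | Φ(−1.89) = 2.9% | 1.2 |

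**5. Effect on the primary contrast.** Assume also that inverse responders have SR-like sodium. Their share of the unsigned SS group is inverse/(p + inverse). At 50% this is 0.048/0.548 = 8.7% to 0.106/0.606 = 17.4%, and the 6 mmol/L difference becomes 5.48 to 4.95. At 74% it is 1.4% to 3.8%, and the difference becomes 5.92 to 5.77. Approximate power in these four cases is 95.0% to 98.6%. Widening the SD to 4-10 mmHg brings the lowest value to 89%.

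**6. The literal signed SAP cutoff.** Under the same model only the inverse responders in step 4 would be labelled SS, and every true responder would be SR.

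**The case against.** A reader might infer that the endpoint has no direction at all, or that the plan will label inverse responders salt sensitive. The documents do not support that.

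- The SAP's classification rule uses the word reduction, which is a direction. Tied to salt depletion, its sensible meaning is a fall in pressure on low salt, so participant B is SR.
- The protocol does not count any change whatever. It orders the comparison as high salt relative to low salt, and in that order B scores −7 and is NSS.
- The SAP phrase stands beside mmHg and speaks of units, so mmHg rather than percent is at least as natural a reading as an absolute value.
- With the sign kept, the reversed order is largely a reporting convention, because two-sided conclusions do not change.

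All of this stands. It shows what was probably meant, but does not supply a formula. The protocol never states a sign, the SAP formula taken with a 5 mmHg cutoff selects the wrong people, and the one sentence with a direction has to be repaired by the reader.

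A larger loss can also be modelled. If sodium is linear in signed Δ with r = 0.4, an unsigned Δ shrinks the SS-NSS gap by 24-43% at 50% prevalence (SD 6-8) and by 6-14% at 74%. That r is in neither document. At 50% it implies a signed gap of 1.596 × 0.4 = 0.64 SD, against 6/4 = 1.5 SD in the plan. I do not rely on it.

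**Conclusion.** The rule is wrong as written because it is inconsistent. The protocol's order, the SAP formula and the SAP cutoff cannot all be followed literally, and the text does not fix group membership or coefficient signs for the variable that defines salt sensitivity. The likely intention is recoverable and excludes inverse responders.

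If an unsigned value were used, about 2-4 of 40 participants would be mislabelled at 50% prevalence and about 0.4-1.2 at 74%. These counts rest on an assumed normal distribution and SD of 6-8 mmHg. Power under the plan's 6 ± 4 stays high, so the case rests on reproducibility and correct labelling rather than lost power.

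**What to change.** Put one signed definition in Protocol 9.0, Protocol 11.0 and both places in SAP 6.1 (Blood Pressure Measurements and Aim 1):

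- Δ is pressure at the high-salt visit minus pressure at the low-salt visit, in mmHg, positive when pressure is higher on high salt.
- SS if Δ ≥ +5 mmHg; otherwise NSS/SR, including all negative values.
- The signed Δ enters every regression and is never folded to a magnitude.
- Delete the SAP's phrase about absolute units and the wording "≥ 5 mmHg reduction in Δ BP depletion", and restate the SR rule to match.

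The same edit should name one pressure, since the protocol uses mean arterial pressure and the SAP sentence says mean arterial systolic pressure. The sign change costs wording in four places, with no new data or visits, and should be made before analysis.
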